5.3 Randomization Procedures

Randomization will be used only for the pilot RCT. Only participants who express interest in using LYNX, meet eligibility criteria, provide informed consent, and complete a baseline assessment will be eligible for randomization. Subjects will be randomized 2:1 into either the LYNX intervention arm (N=40) or control arm (N=20).

The 2:1 allocation will allow us to efficiently gather additional data on app utilization. Randomization will be based on a pre-generated list created by the Analytic Core, with random blocks of size three or six, and stratified by site (Tampa, Chicago) and age (15-18, 19-24). After consent and baseline survey completion, the participant will be randomized (assigned to the next available random allocation). **LYNX Intervention Condition:** Individuals who receive LYNX will be given brief instructions on the purpose of the app, how to access it, and an overview of how to use it. Participants will be encouraged to explore all components of the app and use it routinely. **Standard of Care Condition:** Following screening, participants in both conditions will receive standard of care prevention material consisting of provision of information regarding recommendations for HIV testing and referrals to local HIV testing sites and prevention services.

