10.1.3 Pilot RCT (Aim 3)

Response rates to follow-up surveys will be tabulated by recruitment venue and respondent characteristics to help understand potential sources of bias. We will characterize the study population using descriptive statistics and compare the intervention and control groups at baseline using t-, Wilcoxon, and chi-square tests. Point estimates for mean SUS score ≥ 50 and for proportion accessing the app >0.60 will be considered the minimum criteria for acceptability and feasibility, consistent with industry standards.^{49,50} A secondary feasibility outcome will be achieved if $\geq 50\%$ of participants who open the app complete their personalized risk score at least once.

The secondary outcomes of preliminary efficacy of the LYNX app to increase HIV/STI testing (any testing over follow-up) and PrEP uptake (as described above) will be evaluated using unadjusted risk ratios for each outcome. If there is evidence of divergence from balance in measured baseline covariates (i.e., failure of randomization), post-hoc analyses using Poisson regression with robust standard errors will be used to estimate adjusted risk ratios. Outcome variables will represent any HIV testing and any PrEP uptake over the follow-up period. Separate models will be estimated for each outcome.⁵²

With 60 participants randomized 2:1 to intervention: control, and 10-20% attrition, we will have 80% power to detect 37-42 percentage point increases in HIV testing and PrEP uptake, depending on rates in controls. The lack of precision and large minimum detectable effects, typical of pilot studies, will entail careful interpretation of study results in the light of overall patterns, plausibility, and findings from other mHealth studies.

Qualitative data from exit interviews will be analyzed by the LYNX team using the methods described in Aim 1 and will inform efforts to finalize app revisions and prepare for efficacy evaluation of the app.

Note: Any deviations from the analysis plans outlined above or in the sections that follow will be documented and justified in the Statistical Analysis Plan developed for this protocol.

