10.2 Missing Data

Several procedures will be used to conduct data analysis when data for either outcomes or covariates are missing. The first step will be to assess the extent and pattern of missing data. If data are missing for only a few cases, then data analysis will be conducted only on study participants with complete data. However, when such a strategy would result in loss of data from a substantial proportion of participants, or if this approach would lead to biased or inaccurate results, then some form of imputation will be performed. The form of imputation used will depend on the nature of the data that are missing. For example, data that are collected repeatedly might be imputed using the “last value carried forward” method; and in some instances, interpolation between neighboring points might also be used.

When the primary endpoint is missing, one data analysis will be conducted using only cases with the endpoint. Subsequent analysis will be done where missing endpoints are imputed. Hot-deck imputation or regression imputation may also be used in this context.

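### Section 10.2 calls for imputation when loss is substantial but names only single-fill methods and no way to carry imputation uncertainty into the standard errors; within-arm hot-deck or regression fills would make the arm comparisons look too precise

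*Combined protocol and SAP*

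**What the plan says.** Section 10.2 covers missing outcomes and covariates. It starts by assessing how much is missing and in what pattern, and uses complete cases if the loss is small. If the loss is substantial or complete cases would mislead, "then some form of imputation will be performed". For repeated measures it offers last value carried forward and interpolation as examples. For a missing primary endpoint it runs complete cases first and then an analysis with imputed endpoints, adding: "Hot-deck imputation or regression imputation may also be used in this context".

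The section does not mention multiple imputation, the number of imputations, a variance method, or whether donors or the regression model are specific to the arm.

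In section 10.1.3 the arm comparisons of testing and PrEP uptake "will be evaluated using unadjusted risk ratios for each outcome". The primary endpoints, mean System Usability Scale (SUS) score and app opening, are judged by point estimates against thresholds, with no test. Survey response will be "tabulated by recruitment venue and respondent characteristics"; randomised arm is not named.

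**The concern.** A single hot-deck or regression fill brings the data set back to 60 men. Unless the analysis corrects for this, its standard errors are those of 60 observed outcomes when only 48 to 54 were seen. A random hot-deck also adds the noise of drawing donors, which the usual standard error ignores.

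Section 10.2 turns to imputation when loss is substantial, which is when the distortion is largest. The testing and PrEP risk ratios are the trial's evidence of preliminary efficacy. An imputed result that looks sharper than the complete-case one could be given more weight than it deserves.

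Response by arm matters for a related reason. The intervention arm has an app with reminders and the control arm has a site list and brochure, while the outcomes are self-reported online. Different response by arm is plausible, and that breakdown bears most directly on bias in the arm comparison.

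**Working it through.** **Inputs.** 60 men randomised 2:1, 40 and 20 (5.3). Attrition of 10-20% (10.1.3) leaves 36 + 18 or 32 + 16. Analysis is by unadjusted risk ratio (10.1.3). The plan does not state control rates or alpha, so I assume rates of 0.10-0.50 and two-sided 0.05. I also assume loss at random and equal by arm.

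**1. The plan's own figure.** Section 10.1.3 says: "we will have 80% power to detect 37-42 percentage point increases in HIV testing and PrEP uptake". The statement already allows for the attrition above, and the control rates behind its range are not given. I solved for p2 in

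Φ[(p2 − p1 − 1.96·SE0)/SE1] = 0.80,

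with SE0 the pooled and SE1 the unpooled standard error. Over control rates 0.10-0.50:
- 18 + 36 observed: 35.9-39.2 points
- 16 + 32 observed: 37.6-41.5 points
- 20 + 40, no loss: 33.8-37.4 points

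The stated 37-42 is consistent with the numbers left after attrition. The plan's own precision statement therefore matches complete cases, and a fill back to 60 would claim more.

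**2. Large-sample formula.** Let d be the missing fraction and R the ratio of true to naive variance. The false-positive rate is 2[1 − Φ(1.96/√R)].
- Single within-arm random hot-deck: R = 1/(1−d) + d. At d = 0.2, R = 1.25 + 0.20 = 1.45, √R = 1.204, 1.96/1.204 = 1.628, giving 10.4%. At d = 0.1, R = 1.211, giving 7.5%.
- Within-arm deterministic regression (mean) fill, naive variance taken from the filled data: R = 1/(1−d)². At d = 0.2, R = 1.5625, giving 11.7%. At d = 0.1, R = 1.235, giving 7.8%.
- The same fill with the ordinary binomial variance: R = 1/(1−d) = 1.25 at d = 0.2, giving 8.0%.

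**3. Simulation at the trial's size.** 40 against 20, 20% missing, no true effect, 200,000 trials per setting. Entries are false-positive rates (%).

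| True rate | Risk ratio, complete cases | Risk ratio, within-arm hot-deck | Chi-square, complete cases | Chi-square, within-arm hot-deck |
|---|---|---|---|---|
| 0.10 | 0.7 | 2.8 | 3.7 | 8.4 |
| 0.20 | 2.1 | 5.8 | 4.8 | 9.9 |
| 0.30 | 3.1 | 7.9 | 5.3 | 10.5 |
| 0.40 | 3.4 | 8.5 | 5.1 | 10.8 |
| 0.50 | 3.9 | 8.8 | 5.2 | 11.2 |

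The risk ratio uses the Wald test on the log scale. At a true rate of 0.16 the hot-deck gives 4.9%. Under no effect, coverage of the 95% interval is 100% minus the entry: at rates of 30-50%, about 91-92% after hot-deck and 96-97% for complete cases. At 10% missing and the same rates, hot-deck gives 5.6-6.4% for the risk ratio and about 8% for chi-square. A within-arm mean fill with binomial variance at 20% missing gives 1.7-7.1% for the risk ratio and 7.9-8.7% for chi-square.

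**4. The other named or possible methods, 20% missing.**
- Hot-deck with donors pooled over arms: chi-square 4.0-5.4%, no inflation. But it shrinks a true difference by the factor (1−d). With true rates of 60% and 30% the observed pool has rate (40×0.60 + 20×0.30)/60 = 0.50. The filled arms become 0.8×0.60 + 0.2×0.50 = 0.58 and 0.8×0.30 + 0.2×0.50 = 0.34, so 30 points become 24. Coverage falls to about 89%.
- Last value carried forward: chi-square 3.9-5.0%, no inflation. Its weakness is bias.
- Interpolation was not simulated. It needs a later observed value, so it cannot fill a missing final visit.

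**5. SUS mean in the LYNX arm, 8 of 40 missing.** A nominal 95% interval covers 89.7% after hot-deck and 88.5% after mean fill.

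**6. The remedy.** With hot-deck multiple imputation (approximate Bayesian bootstrap, 20 sets, Rubin's rules) and a Wald test on the risk difference at 20% missing, the false-positive rate is 6.8-7.5%. Complete cases give 6.0-6.8% and a single hot-deck 12.6-13.2% with the same test.

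**The case against.** Several counter-arguments have weight.

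- **The hot-deck and regression sentence concerns the primary endpoints.** These have no test, and app opening comes from app analytics, so survey non-response does not make it missing. This stands: no test error rate applies there. But the first paragraph of 10.2 covers all outcomes and commits to imputing when loss is substantial, so the secondary comparisons are within its reach.
- **The wording is permissive and a separate analysis plan is foreseen.** The methods are examples or options, and 10.1.3 sends deviations to a Statistical Analysis Plan. That the fill would be analysed as observed data is an inference from silence: the text neither says so nor rules it out.
- **A reader might infer that every named method doubles the false-positive rate.** The documents do not support this. Carry-forward and pooled donors show no inflation, interpolation was not tested, and whether donors would be arm-specific is not stated.
- **The 11% figure belongs to chi-square.** Section 10.1.3 names that test only for baseline comparisons. For the planned risk ratio the excess over nominal is smaller, and absent at low event rates. The PrEP figures in section 1.1 are low: 1.7% ever use and 16% uptake in one demonstration study.
- **20% attrition is not 20% missing outcome.** The outcome is any event over follow-up, so a week-12 yes settles it. Discontinuers are asked to complete week-24 procedures and late surveys are accepted. If only week 24 is missing for 20%, week-12 answers are kept and the testing rate is assumed constant, the hot-deck risk-ratio rate falls to 6.0-6.8%.
- **Complete cases already perform well.** When loss is unrelated to outcome, multiple imputation gains nothing over them. Its use is as an honest second analysis when loss depends on observed data.

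**Conclusion.** The gap is real but conditional. Section 10.2 commits to imputing under substantial loss, names only methods that are single-fill in their usual form, and gives no way for imputation uncertainty to reach the standard errors.

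The distortion arises if a single within-arm hot-deck or regression fill is used for the testing and PrEP comparisons without a variance correction. For hot-deck at 20% missing and true rates of 30-50%, the risk-ratio false-positive rate then more than doubles relative to complete cases, but exceeds the nominal 5% by only 3 to 4 points. At 10% missing the excess is about one point, and at event rates of 10-16% there is none. Pooled donors bring dilution and carry-forward brings bias, which are different faults.

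It would be wrong to conclude that the primary feasibility and acceptability decisions have an inflated error rate. They rest on point estimates, and only a reported interval, such as that for the SUS mean, would be too narrow.

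These sizes assume two-sided 5% tests, loss at random and equal by arm, and assumed event rates, since the plan gives none. In a pilot that already asks for cautious reading, this is a modest correction, worth making because it is cheap.

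**What to change.** In section 10.2:
- Keep complete cases as the main analysis.
- Replace hot-deck, regression, interpolation and carry-forward fills with multiple imputation, at least 20 sets, combined by Rubin's rules.
- Put arm in the imputation model or impute within arm, and say which.
- Keep the predictor set small. Only about 16-18 controls will be observed, and at a 30% rate 16 controls give about 5 events (16 × 0.30 = 4.8).
- Count a reported week-12 yes directly as an event for any testing over follow-up, and do not impute it.
- Add best- and worst-case bounds by arm. At 20% missing they span 8/40 + 4/20 = 40 points on the risk difference, and at 10% they span 4/40 + 2/20 = 20 points. They are wide, but they show what the data alone can exclude.

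In section 10.1.3, tabulate week-12 and week-24 response by randomised arm as well as by venue and characteristics.

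The cost is a few sentences, a little more code, and intervals slightly wider than a single fill would give. No data collection changes.

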11.0 HUMAN SUBJECTS

This study will be conducted in compliance with the protocol, ICH Good Clinical Practice guidelines, and 45 CFR Part 46.

11.1 Participants' Confidentiality

All records with personally identifying information will be kept in a locked, limited access area (such as a locked file cabinet) or in a secure limited access database (such as SMART). All computer entry and networking programs will be done with coded numbers only. Clinical information will not be released without written permission of the participant, except as necessary for monitoring by the MC or NICHD.

Every effort will be made to ensure that study participants are protected from risks.

Breach of Confidentiality: A potential risk to participants is violation of confidentiality. We will take the utmost caution to protect the confidentiality of all responses. We will minimize this risk by maintaining confidentiality and discretion throughout all iTech research procedures and data management and analysis.

We will inform participants to only use first names or nicknames during the focus groups and that all information discussed during the focus groups will be used to develop general themes and will not be linked to any specific person. The focus groups will be conducted by study team members with extensive experience in ensuring the safe conduct of group discussions. We also ask participants not to discuss any information from the focus groups once they leave. Participants also have the right at any time to decide not to participate or answer questions.

All audio/video files will be kept confidential and stored in a limited access folder on Box, accessible only to study staff. All members of the research team will be trained in confidentiality and have signed confidentiality agreements. A professional transcription service, experienced in the handling of confidential data, will be used to fully transcribe verbatim all audio/video files.

Study staff at all sites are trained in confidentiality and have signed confidentiality agreements. Study staff have been trained in ethical human subjects research techniques in order to minimize participant risk as much as possible.

Participants may be concerned about the security of their data, particularly since it is collected and stored electronically. The Analytic Core has significant experience developing security protocols for internet-based studies, and we will take a variety of steps to ensure participant security, including using a dedicated server behind a firewall, encryption of data, separation of identifiers from responses, and password-protected access to data. Therefore, we believe that this risk will be minimal.

All data collected by the LYNX app will be secured through the following security measures: All data stored on a user's device will be encrypted, as will all data stored in the research database. The encrypted MySQL database will be stored in the Amazon Web Service Cloud (AWS), a secured environment that supports HIPAA compliance (as well as Business Associate Agreements) and has been approved for US government projects that include highly sensitive personally identifiable information. All data transfers between a user's mobile device and the research database will be

encrypted and transmitted via Secure Socket Layer (SSL); and external systems will only have access to specific fields (or objects) necessary to accomplish the research objectives. Data download access will be on an as-needed basis to designated individuals within the research organization which may be limited by IP address, further ensuring data is not downloaded by unauthorized parties. All administrative interfaces are accessed through SSL ensuring that data are safe, secure, and available only to registered users.

Participants interested in ordering home STI testing kits (i.e. CareKits) or condoms/lubricants will be directed to a separate data collection instrument on SurveyGizmo. After selecting the items they would like to order, participants will be asked to provide names, mailing addresses, and preferred contact information (email or cell phone number for SMS). This personal information will be used only for the purposes of fulfilling the order, confirming participation in the study and returning lab testing results, and will be kept in a password-protected file on a secure drive. STI testing lab results will be posted to HIPAA-compliant web-based platform SMART in Aim 3 for participants to access (see Section 7.4. 3 for more information on SMART).

11.2 Certificate of Confidentiality

This research specifically targets a vulnerable population, children (YMSM ages 15-17). We will take every available step to minimize the risk of identifying/linking data being subpoenaed, stolen, or inadvertently released. First, the iTech will request a Certificate of Confidentiality from the NIH. Second, all research staff members are required to complete ethical clearance certification regarding protection of human's subjects through their relevant IRBs. Third, all studies will have documented procedures to safeguard against the risk of the linking information being stolen by keeping such information in a locked spaces to which only essential study personnel who have completed CITI certification for human subjects research ethics training (<http://citiprogram.org>) will have access.

A Certificate of Confidentiality for the iTech will be sought prior to enrolling participants. As noted on the NIH website (<http://grants.nih.gov/grants/policy/COC/faqs.htm#187>), a Certificate of Confidentiality will help the research team "...avoid compelled 'involuntary disclosure' (e.g., subpoenas) of names and other identifying information about any individual who participates as a research subject (i.e., about whom the investigator maintains identifying information) during any time the Certificate is in effect." We have applied for and received Certificates of Confidentiality for other NIH-funded research projects, and given the sensitive nature of the data collected for this project, do not foresee difficulty securing one for this study.

11.3 Risks and Benefits

11.3.1 Risks

Risks to participants in this research study may include:

The measurements that are involved in this study require fingerstick to collect blood samples. This procedure may cause local discomfort, bleeding, or bruising; rarely small clot or infection can occur at the fingerstick site. This measurement should not be considered greater than minimal risk in and of

itself given its routine use in general health care delivery.

Participants may also feel discomfort or pain with collection of pharyngeal or rectal STI specimens. This risk will be minimized through providing written and video instructions to participants.

To minimize the risk of participants feeling uncomfortable about answering personal questions, we will use Computer Assisted Self Interview (CASI) methods for the study's surveys. In CASI, participants read survey questions on a laptop computer or mobile phone and use a combination of mouse click and keyboard/touchscreen entry to input the answers themselves. Study staff may be available to assist participants with questions or technical difficulties on the CASI. Participants will also be able to refuse to answer any question that makes them uncomfortable. In-depth interviews will be conducted face-to-face or online depending on the research project.

To minimize risks to confidentiality, we will secure study data with all appropriate physical, electronic, and operational protections. Data will be stored in a physically secure environment. All data files will have encryption and strong password protection. Any identifiable data will either be stored on Emory University's secure servers, on fully encrypted computers, or on paper forms securely stored at the study sites. CASI surveys and online eligibility screening will take place on an encrypted commercial survey website, SurveyGizmo (<http://www.surveygizmo.com/survey-software-features/secure-link/>). This site has been used by the investigators for thousands of online surveys with MSM with no data security breaches. Access to data will be on a role-based standard; only those study staff who require access to each type of data to complete their study-related roles will be allowed access. All study staff will be trained in security and confidentiality procedures, and will sign a confidentiality agreement before receiving access to any participant data.

We will also develop procedures to minimize indirect disclosure that a participant is participating in an HIV-related research study, or a study that enrolls MSM. For each mode of contact information, we will ask specifically whether anyone else potentially has access to that mode of communication, and if it is acceptable to leave a non-specific message about participation in a health study. No study-related messages will ever mention HIV prevention or the nature of the research study. Additionally, all scripts for email, text message, and telephone contact with participants will be reviewed and approved by the UNC-CH IRB before being used for contact with participants.

We use SSL encryption for transfers of information online, and SurveyGizmo has a business partner HIPAA agreement with Emory. SurveyGizmo's servers are HIPAA compliant.

The Analytic Core will use Dedoose software to perform all qualitative analyses. Dedoose is a web-based application for organizing and analyzing textual, audio, and video data (qualitative) along with outstanding functionality for their integration with survey, test score, ratings, and demographic data (quantitative). Dedoose employs the highest levels of data encryption available for a web application in all data storage, back up, and transmission. Dedoose allows for project specific encryption feature. When using this feature, only [name] or her designee will hold the additional encryption key needed to be entered in order to view the project. This gives [name] exclusive control over who can view the project under any circumstances.

In addition to a Certificate of Confidentiality, we will protect participants in the following ways:

1. Breach of confidentiality. We will take every precaution to minimize risks to study participants. All Analytic Core research staff members are required to complete ethical clearance certification regarding protection of human subjects through UNC-CH or Emory University. We also have a strong data and safety monitoring plan in place to protect participants. Adverse events will be reported to the UNC-CH and Emory IRBs, individual research PI institutional IRBs, and SRV site-specific IRBs using Adverse Event Reporting Forms created by the Analytic Core. Reports will be sent within 24 hours of notification by the PIs. Annual updates on enrollment and retention will also be sent to the IRBs.

All data collection will take place in secure and supervised clinical settings. All study personnel names on this application have completed training and received certification in Human Subjects Research Protection (CITI Program) and HIPAA regulations. They will continue to renew this training in compliance with institutional policies.

